Building upon this experience, a prospective study of 15 patients from Harvard demonstrated that neoadjuvant short course RT using 25 Gy in 5 fractions to the pancreatic bed and regional lymph nodes using proton therapy and concurrent capecitabine was feasible and well tolerated. Acute grade 3 toxicity was noted in 4 of 15 patients. 11 of 15 patients underwent surgical resection but no patients experienced delays or exclusion from surgery due to toxicity from neoadjuvant treatment. Evaluation of 30 day post-operative results showed no deaths or anastomotic leaks. 9 of 11 patients who underwent surgery had R0 resections and 10 of these patients were able to receive post-operative gemcitabine. After a median follow up of 12 months, one year overall survival was 75% for the entire group. Of 11 surgical resected patients, 10 are still alive at last follow up. Of 15 patients treated with neoadjuvant therapy, only 1 patient with a positive surgical margin experienced local progression. No patient experienced nodal or regional failure but 8 patients developed metastatic disease.

A similar study was repeated, also at Harvard, using photon (conventional x-rays) instead of proton radiation therapy. However, compared with the proton study a higher rate of fibrosis (63% vs. 27%) was noted during surgery leading to a mean increase in operative time of 69

minutes. Dosimetric comparisons revealed that patients undergoing photon irradiation had significantly increased low dose radiation exposure to the abdominal organs. Due to this complication, the study was terminated after accrual of 10 of 12 planned patients.

While the Harvard study with neoadjuvant proton therapy achieved excellent results, protons are not widely available at most centers including ours. Therefore, we believe that there is a need for continued investigation of neoadjuvant photon radiation therapy for pancreatic cancer. We hypothesize that delivering high dose photon radiation to the gross disease using stereotactic localization (SBRT) without elective nodal irradiation can effectively reduce local recurrence while minimizing the fibrosis noted in the Harvard Photon study.

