## **9. DATA ANALYSIS AND MONITORING**

The purpose of this pilot study is to determine feasibility of preoperative SBRT followed by surgical resection at URMC and to determine its safety and tolerability in a small population of patients. For this phase 1 trial, we plan to enroll 18 patients over 1-2 years with a goal of 12 evaluable cases. This is a generally accepted number of patients for phase 1 trials and will minimize the risks to patients in case the treatment is found to be unsafe. We will stop recruitment and analyze the safety data if there appears to be any grade 3 or greater toxicity on any subject that can be directly attributed to SBRT or if any patients are made ineligible for surgical resection solely due to toxicities from SBRT.

In the case where any patient becomes ineligible for resection due solely to toxicity from SBRT, the study will be immediately closed to accrual. We will stop recruitment and any patient who has not started radiation therapy will have their planned radiation treatment canceled. A patient who has started radiation therapy will undergo an individual discussion with [name] about the risks and benefits of continued treatment.

If a patient experiences grade 3 or greater toxicity directly attributable to SBRT that is reversible and ultimately able to undergo resection, we will analyze the event and attempt to prevent/reduce the adverse event from taking place again. We will discuss the risks and benefits of continued recruitment into the study with our co-investigators and determine whether or not to continue the study. If we believe that modifications can be made that will reasonably reduce the risk of a future event from occurring, we will continue recruitment to the study.

The investigators plan to evaluate the rates of acute toxicity after 12 patients have been enrolled and undergone SBRT and surgical resection. Long term safety and efficacy will be evaluated after all 12 patients have undergone surgical resection and have either been followed for at least 6 month or have died. The primary investigator, [name] will have access to all of the study data.

The Cancer Center Data & Safety Monitoring Committee will monitor the study for safety. Study

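### After a reversible grade 3+ SBRT toxicity in a patient who still reaches resection, Section 9 lets the investigators resume recruitment on their own judgement, with no cumulative event limit and no required DSMC decision

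*Combined protocol and SAP*

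**What the plan says.** Section 9 of the combined protocol and SAP states the sample size as "we plan to enroll 18 patients over 1-2 years with a goal of 12 evaluable cases" and supports it only by convention: "This is a generally accepted number of patients for phase 1 trials". It names no unacceptable toxicity rate.

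The safety rules in Section 9 work in three steps.

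- **Pause.** "We will stop recruitment and analyze the safety data if there appears to be any grade 3 or greater toxicity on any subject", where the toxicity is directly attributable to SBRT. Loss of eligibility for surgery solely through SBRT toxicity triggers the same pause.
- **Closure.** "In the case where any patient becomes ineligible for resection due solely to toxicity from SBRT, the study will be immediately closed to accrual". Radiation not yet started is cancelled.
- **Restart.** For a patient with "grade 3 or greater toxicity directly attributable to SBRT that is reversible and ultimately able to undergo resection", the team analyses the event and discusses the "risks and benefits of continued recruitment into the study with our co-investigators". The test for continuing is "If we believe that modifications can be made that will reasonably reduce the risk of a future event from occurring".

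Acute toxicity rates are evaluated once 12 patients have had SBRT and resection.

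The DSMC monitors safety. It receives quarterly progress reports with the adverse event spreadsheet. Events that are serious, related and unexpected are reported within 10 calendar days; the DSMC Chair then decides whether more needs to be done and an interim meeting may be called. Serious events that are related but expected go to the quarterly meeting. Appendix C has a field for DSMC recommendations. Section 6.5 stops SBRT in the individual patient who has a serious adverse event or a grade 3 or higher treatment-related toxicity.

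**The concern.** The restart test looks at one event at a time and rests on belief. It has no count, denominator or rate, so it can be met after the first event and again, in the same words, after the third or the sixth. Followed exactly, it permits any number of reversible grade 3+ events in resected patients without accrual having to close. The decision lies with the people running the trial. The independent committee already in place has no stated part in it and no numerical criterion to apply.

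This matters because safety and tolerability are the trial's primary question. If the true rate were high, the plan would record the events as they came, but nothing would oblige anyone to weigh their accumulated number before 12 patients had been treated and resected.

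There is also a smaller gap. The pause covers every attributable grade 3+ event, but the follow-on branches cover only loss of resection, or a reversible event with resection. An irreversible event in a patient who is still resected pauses recruitment, and the text does not say what happens next.

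**Working it through.** **The plan's own figure.** No derivation is given for 12 or 18, so there is nothing to reproduce. The ratio 12/18 implies that one third are not evaluable. For comparison, the 11 of 15 resected in the proton study (Section 1) would give 12 ÷ (11/15) = 16.4, that is 17. No stopping boundary or error rate is stated.

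**Inputs on toxicity.** Section 1 gives two acute rates.

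- Short-course protons with capecitabine: "Acute grade 3 toxicity was noted in 4 of 15 patients", that is 4/15 = 26.7%.
- SBRT for locally advanced disease after induction chemotherapy: 0 of 73 with acute grade 3 or higher. The exact two-sided 95% upper limit is 1 − 0.025^(1/73) = 4.9%.

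The regimens and populations differ from this trial's, so neither is a direct estimate for it. The true rate is therefore treated as an assumption and varied from 5% to 26.7%.

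**Formulas.** With n patients receiving SBRT, independent events and a constant rate p:

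- P(at least one) = 1 − (1 − p)^n
- P(five or more) = 1 − Σ C(n,k) p^k (1 − p)^(n−k), k = 0 to 4

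Example: at p = 4/15 and n = 18, 1 − (11/15)^18 = 0.996.

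| Assumed true rate | At least one in 12 | At least one in 18 | Three or more in 18 | Five or more in 18 | Expected in 18 (18p) |
|---|---|---|---|---|---|
| 5% | 46% | 60% | 6% | 0.2% | 0.9 |
| 10% | 72% | 85% | 27% | 3% | 1.8 |
| 20% | 93% | 98% | 73% | 28% | 3.6 |
| 26.7% | 97.6% | 99.6% | 90% | 55% | 4.8 |

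The columns for three or more and five or more, and the expected counts, assume that every pause ends in restart, that no event blocks resection (which would close accrual), and that the modifications made after each pause do not change the rate.

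**What a cumulative limit would do (illustration only, not a proposed rule).** Take a uniform prior on the rate and look after each patient from the third. Close when the posterior probability that the rate exceeds 20% is above 0.9. The limits are 2 events by patient 5, 3 by 8, 4 by 12, 5 by 15 and 6 by 18. Exact enumeration gives:

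| True rate | Probability of closure within 18 | Mean number treated, all trials |
|---|---|---|
| 5% | 2.5% | 17.7 |
| 10% | 10% | 16.7 |
| 20% | 38% | 13.5 |
| 26.7% | 59% | 11.0 |
| 40% | 90% | 6.8 |

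The last column counts trials that never close as 18 patients. At 40%, the mean among trials that do close is 5.5. The 20% reference is assumed; the documents give no such figure.

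**The case against.** A reader might infer that nothing in the plan closes the study, or that patients have no defined protection. The documents do not support either reading. One patient who loses resection solely through SBRT toxicity closes accrual at once, and Section 7.2 lists delayed or prevented resection first among the risks. Recruitment pauses at the first attributable grade 3+ event, and Section 6.5 stops SBRT in the affected patient. The DSMC can act on its own judgement. Because Section 6.5 anticipates no serious treatment-related events during or just after SBRT, such an event would plausibly count as unexpected and reach the DSMC quickly.

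A reader might also infer that any event after resection falls outside the rules. It does not: the pause has no time limit, and a reversible event in a patient already resected fits the restart paragraph. Only the irreversible event lacks a next step, and read strictly the text then gives a pause with no permission to resume, which is conservative.

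Nor is a pause near certain on the documents' evidence. That reading takes 4/15 from a proton and capecitabine regimen that also treated regional nodes, and passes over 0/73 with SBRT. At 5%, the chance of any event in 18 is 60%, and of five or more 0.2%.

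Finally, a formal boundary in a small, single-arm, descriptive pilot is partly a matter of preference.

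What stands after all this is the restart rule itself. None of these safeguards limits the number of reversible events in resected patients or requires DSMC agreement before restart. The wide gap between the two cited rates is a reason to fix a limit in advance.

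**Conclusion.** The point holds for one defined group: reversible grade 3+ SBRT toxicity in patients who still reach resection. For them, the rule as written depends on investigator belief, has no cumulative limit and requires no DSMC decision. This is a weakness in a stated rule, not a missing detail, and it should be corrected.

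The size depends on a rate nobody yet knows. Over assumed rates of 5% to 26.7%, the restart decision would be reached at least once in 60% to 99.6% of trials of 18, provided the event is reversible and resection follows. Five or more events, with no closure required, would occur in 0.2% to 55%. The practical risk is small if the rate is near the upper limit from the SBRT series and substantial if it is near that of the proton study. All figures assume that 18 patients receive SBRT, that patients are independent and that the rate is constant. The two cited rates are acute only, whereas the pause is not restricted to acute events.

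**What to change.** In Section 9:

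1. Keep the first-event pause and the existing closure rule unchanged.
2. Require a documented decision by the existing DSMC before recruitment resumes after any grade 3+ pause.
3. Prespecify a cumulative number of attributable grade 3+ events, by number treated, at which accrual closes or the DSMC must decide on closure. Report its operating characteristics over a range of true rates. The sponsor and the DSMC set the acceptable rate.
4. State which branch covers an irreversible grade 3+ event in a patient who is resected.

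This takes one paragraph and a small table, and uses a committee already in place. The cost in operation is a short delay at each restart and some chance of closing early when the true rate is low. Under the illustrative boundary that chance is about 2.5% at a true 5% and 10% at a true 10%; the actual figures will depend on the limit chosen.

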## 6.3 Documentation of Adverse Events

All adverse events, whether observed by the Investigator, elicited from or volunteered by the subject, will be documented. Each adverse event will include a brief description of the experience, the date of onset, the date of resolution, the duration and type of experience, the severity, and the relationship to SBRT, contributing factors, and any action taken with respect to the planned radiation therapy. In addition, any toxicity leading to radiation treatment break and delay in surgical resection beyond 3 weeks post SBRT will be noted.

All patients are expected to undergo surgical resection within 3 weeks after radiation therapy. Any Intraoperative complications including blood loss, total operative time and amount of fibrosis noted by the surgeon will be recorded in the operative report. Post-operative complications including delayed wound healing, blood loss, infection, length of hospital stay, incidence of pancreatic leak, hospital readmissions for complications will also be recorded. Appendix A lists the data the surgical oncology team is responsible for recording.

Treatment related late complications including but not limited to duodenal and intestinal ulceration, perforation, gastritis, bowel adhesions and obstruction, will be recorded at follow ups up to 5 years after treatment.

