## 6.5 Treatment Modification due to adverse events

We do not anticipate any serious treatment related adverse events will take place during or immediately following SBRT treatment. We expect that the most common acute toxicities of radiation therapy will be mild nausea, fatigue and loose bowel movements.

Patients will finish planned radiation if they experience up to grade 2 treatment related toxicity. If patients develop any serious adverse event or any grade 3 or higher treatment related toxicity, SBRT radiation will be stopped and the patients will proceed directly to surgical resection if deemed appropriate by surgical oncology.

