## 7.2 Risks of Participation

- a) Preoperative SBRT could cause toxicities that could delay or even prevent surgical resection which is the most important treatment for resectable pancreatic cancer. However, previous studies have demonstrated that the vast majority of patients who undergo preoperative radiation can safely undergo surgery in a timely fashion.
- b) Radiation therapy can cause both acute and delayed side effects. Acute side effects that take place during or immediately after treatment can include fatigue, nausea, vomiting, diarrhea, loss of appetite and weight loss. These effects are expected to be uncommon and can be managed with supportive care such as anti-nausea or anti-diarrheal medicines. Delayed side effects can take place months to years after radiation and can include delayed wound healing, scar tissue formation and bowel obstruction and structuring. These effects are expected to be very rare. These effects are expected to be similar or decreased compared with the toxicities associated with conventional radiation.
- c) There is a risk of invasion of patient privacy. All the information gathered from patient chart or records, including name and any other identifying information will be strictly confidential and will be kept under lock and key. The patients will not be identified nor will any information that would make it possible for anyone to identify the patient be used in any presentation or written reports about this study. Only summarized data will be presented at meetings or in any publications.

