Investigators will conduct continuous review of data and patient safety. The Investigator will submit quarterly progress reports of these data to the Clinical Trials Monitoring Committee for review [Appendix C]. The review will include for each treatment arm/dose level: the number of patients enrolled, withdrawals, significant toxicities as described in the protocol, serious adverse events both expected and unexpected, dose adjustments, and responses observed. The PI maintains a database of all adverse events with toxicity grade and information regarding treatment required, complications, or sequelae. The Investigator will submit a copy of the AE spreadsheet along with the Progress Report to the Clinical Trials Monitoring Committee for review. Actual review dates will be assigned when the 1st patient is accrued.

- Any serious adverse event that is serious, related AND unexpected must be reported within 10 calendar days to both the Safety Coordinator and the RSRB (see RSRB guidelines). The DSMC Chair will determine whether further action is required, and when patient safety is of concern, an interim meeting may be called.
- Serious adverse events that are related AND expected or unrelated AND unexpected will be reported to the Committee for review at the quarterly meeting. SAE reports are expected to include sufficient detail so that the DSMC can determine the severity, toxicity grade, expectedness, treatment required, and a follow up report documenting resolution or if there are sequelae. Unless otherwise specified in the protocol, serious adverse events that require detailed reports (but not necessarily expedited) are expected, related, non-hematologic toxicities of grades 3, 4 or 5.

We plan to publish a descriptive analysis of the results including acute and late toxicity including surgical morbidity. We plan to report oncologic outcomes including median overall survival, progression free survival, local progression free survival and distant progression free survival. Analysis will be using Kaplan-Meier method. Survival time will be measured from the date of diagnosis. A local recurrence will be defined as any evidence of tumor recurrence within the PTV. Whether local recurrence occurred in conjunction with, before or after distant recurrence will be noted.

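### Section 9 pauses recruitment by grade and attribution but sets a reporting deadline only for serious, related and unexpected events, so investigators can restart before the monitoring committee hears of the pause

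*Combined protocol and SAP*

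**What the plan says.** Two sets of rules in Section 9 bear on this point.

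**Recruitment.** The first trigger reads "We will stop recruitment and analyze the safety data if there appears to be any grade 3 or greater toxicity on any subject", provided the toxicity is directly attributed to SBRT. The second is a patient who can no longer have resection purely because of SBRT toxicity; then "the study will be immediately closed to accrual", and radiation is cancelled for those who have not begun it. Neither trigger depends on whether the event is serious or expected. After a reversible event of grade 3 or above in a patient who still reaches resection, the investigators analyse it and look for ways to prevent another. On whether to go on, the text is "We will discuss the risks and benefits of continued recruitment into the study with our co-investigators". It states no committee step.

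**Reporting.** Only one deadline is given: "Any serious adverse event that is serious, related AND unexpected must be reported within 10 calendar days to both the Safety Coordinator and the RSRB". The DSMC Chair then decides whether more is needed, and an interim meeting is possible. The next tier is "Serious adverse events that are related AND expected or unrelated AND unexpected will be reported to the Committee for review at the quarterly meeting". The same bullet says that expected, related, non-hematologic toxicities of grades 3, 4 or 5 need a detailed report but not necessarily a fast one. Progress reports, with the adverse event spreadsheet, are quarterly.

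**Elsewhere.** Section 6.4 sends every SAE to the primary investigator within 24 hours and to the IRB under local policy. The second footnote in Appendix C sends serious events that are unrelated or expected to the RSRB at least annually, and to the DSMC under that committee's own requirements.

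**The concern.** The pause rule sorts events by grade and attribution. The reporting rule sorts them by seriousness, relatedness and expectedness. An event can meet the first and miss the second.

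The two rules need not use the same criteria if the committee enters the process some other way before recruitment resumes. Section 9 gives it no such entry. In a single-center, single-arm study the investigators attribute the event, label it, analyse it and decide whether to reopen. Section 9 names a separate committee to monitor safety. If that committee hears of a pause only at its next quarterly review, its view comes too late to affect the restart.

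**Working it through.** The plan states no figure on this point, so there is none to reproduce. The check sets the triggers beside the reporting routes and then puts an upper bound on the exposure.

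**Step 1. Follow each kind of triggering event to the committee.**

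| Event | Effect on recruitment | Stated route to the committee | Stated timing |
|---|---|---|---|
| SBRT-attributed, grade 3 or above, serious, unexpected | Pause | Safety Coordinator and RSRB, then DSMC Chair | 10 calendar days |
| SBRT-attributed, grade 3 or above, serious, expected | Pause | Quarterly meeting | Next quarter |
| SBRT-attributed, grade 3, not serious under Section 6.4 | Pause | Spreadsheet with the progress report | Next quarter |
| Resection lost through SBRT toxicity, event not serious or labelled expected | Closure | As in the two rows above | Next quarter |

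Only the first row has a deadline. The 24-hour notice in Section 6.4 goes to the primary investigator, and its IRB reporting is not reporting to the committee. Appendix C adds no time limit. The interim meeting is discretionary and is mentioned only with serious, related and unexpected events.

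**Step 2. Ask which of these events can be followed by a restart.** The restart clause covers reversible events of grade 3 or above in patients who still reach resection. The closure trigger has no restart clause. A fatal SBRT event is not reversible. Before surgery it would, on a plain reading, also cost the patient resection and so close accrual; after surgery, Section 9 gives no restart rule for it. For a closure or a death, therefore, the gap is the missing deadline. For a reversible event, it is the missing deadline together with a restart that the investigators decide.

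**Step 3. Bound the exposure after a restart.** Inputs from Section 9: 18 patients, accrual over 1 to 2 years, quarterly review.

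- Enrolments per quarter = 18 / (4 × years).
- Over 1 year: 18 / 4 = 4.5, or 4.5 / 18 = 25% of planned accrual.
- Over 2 years: 18 / 8 = 2.25, or 2.25 / 18 = 12.5%.
- For comparison, enrolments in 10 days: 18 × 10 / 365.25 = 0.49 over 1 year, and 18 × 10 / 730.5 = 0.25 over 2 years.

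The quarterly figures are upper bounds. They assume even accrual, an event just after one quarterly review, and an almost immediate restart. For the closure trigger the figure is zero.

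**The case against.** The best defence is that the pause is already cautious. One event is enough, the investigators act without waiting for anyone, and in the closure case patients who have not started radiation do not receive it. Institutional SAE routing serves a different purpose from a trial's own pause rule, and DSMC or RSRB policies outside these documents may be faster. All of this stands. It limits the point to independent oversight before restart, but it puts no such oversight in the plan.

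Four stronger readings are tempting and are not supported.

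- *Recruitment carries on for a quarter after an event.* It does not; Section 9 stops it. The 2.25 to 4.5 patients apply only after the investigators restart.
- *The protocol contradicts itself on what is expected.* Section 6.3 lists "duodenal and intestinal ulceration, perforation, gastritis, bowel adhesions and obstruction", Section 6.5 says "We do not anticipate any serious treatment related adverse events will take place during or immediately following SBRT treatment", and Section 7.2(b) says of delayed effects "These effects are expected to be very rare". These cover different windows: Section 6.5 the period during and just after SBRT, the other two late or delayed effects. Section 6.3 is a list of what to record and does not define expectedness. Under Section 6.5 an early serious SBRT event would most naturally count as unexpected and take the 10-day route. That narrows the gap. It leaves non-serious grade 3 events and late events, and no section defines expectedness by event and grade.
- *Unrelated and expected SAEs never reach the committee.* The bullets do not name them, but the quarterly review in Section 9 covers expected and unexpected SAEs, and the second footnote in Appendix C covers them too.
- *The cited toxicity rates show how often the pause will occur.* The Background gives acute grade 3 toxicity in 4 of 15 patients, after proton therapy to bed and nodes with capecitabine. For SBRT in locally advanced disease after induction chemotherapy, it gives no acute and 5% late toxicity of grade 3 or above among 73 patients. Neither regimen is this one, so no useful frequency follows.

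**Conclusion.** The point holds as a gap in oversight. By the plan's stated routes, a pause caused by a non-serious grade 3 event, or by a serious event labelled expected, has no deadline for reaching the monitoring committee, and the investigators may restart before it does. At most 2.25 to 4.5 patients, 12.5% to 25% of planned accrual, could be enrolled in that interval. An SBRT-related death labelled expected can also wait for the quarterly meeting, although the restart clause as written does not extend to it.

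This rests on four assumptions: that the Clinical Trials Monitoring Committee and the DSMC are the same body for this purpose, as the use of the DSMC form in Appendix C suggests; that grade 5 means death on the CTCAE 4.0 scale adopted in Section 6.1; that accrual is even; and that no outside policy sets a faster clock. The change should be made because it is cheap and improves safety oversight. It does not call the pause rule itself into question.

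**What to change.** Reconcile the recruitment and reporting rules within Section 9 by adding two statements:

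1. Any event that meets a Section 9 pause or closure trigger, and any SBRT-related death, is reported to the Safety Coordinator, the DSMC Chair and the RSRB within the existing 10 calendar days, whether or not it is classed as serious or expected.
2. After a pause, recruitment does not restart until the DSMC Chair has reviewed that report.

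The second statement is needed because a 10-day notice alone would not stop the investigators reopening sooner. With both in place, no patient is enrolled between a pause and the Chair's review, against the present upper bound of 2.25 to 4.5.

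The change uses the existing committee and clock. It costs a few more expedited reports in an 18-patient study and possibly a short delay before restart. The rest of the SAE routing can stay as it is.
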